#### 2.5.3 Handling of missing values/censoring/discontinuations

If patient's platelet assessment for evaluating the primary endpoint are missing, they will be assessed as non-responder. Patients dropping out early will be considered as early discontinuation or not evaluable, will be considered in the analysis set as non-responders. Thus, missing values are not expected for the primary analysis.

#### 2.5.4 Supportive analyses

Novartis

Reasons for non-response are assessed during the Data Review Meeting and are categorized into these distinct categories:

- 1. Initial response but lost later on, or bleeding, or rescue medication before treatment discontinuation
- 2. Initial response but treatment not discontinued
- 3. Initial response but after treatment discontinuation rescue needed
- 4. Initial response but after treatment discontinuation bleeding
- 5. Initial response but platelet count decreased <30 after treatment discontinuation
- 6. Initial response but response data are missing until W53
- 7. No response at all
- 8. No response data at all

If several reasons apply, the reason that applied first was determined to obtain distinct classes. A frequency table was presented for these reasons of non-response.

Sensitivity analyses and supportive analyses will be conducted in order to provide evidence that the results seen from the primary analysis are robust.

The impact of the analysis assumptions on the result of sustained response off treatment will be assessed as well by repeating the logistic regression model using different populations and ways to handle missing data. These includes:

Using the treatment policy estimand "sustained response based on platelet count only" a) which is defined as maintenance of a platelet count  $\geq 30 \times 10^{9}$ /l starting from cycle 1, 2 or 3 (DEX), or start of tapering at week 20 (ETB+DEX), until Week 53, i.e. no matter if intercurrent events such as bleeding, treatment discontinuation or reinitiation, or rescue treatment occurred. For this estimand the population is used: Patients of the FAS population

b) Using the treatment policy estimand b) for the population: FAS population who completed the study at least until Week 53

Data defining the primary outcome of sustained response off treatment will be further reported descriptively to give the full picture. This will include:

- Platelet counts at treatment discontinuation: sample statistics
- Frequency of patients with complete response at treatment discontinuation; defined as a) platelet count  $\geq 150 \times 10^{9/1}$ 
  - b) platelet count >  $100 \times 10^{9/1}$
  - c) platelet count  $\geq 50 \times 10^{9/1}$
- Timepoint of reaching platelet count  $\geq 150 \times 10^{9}$ /l: Kaplan Meier estimates and curve, censored with date of last study medication/last visit
- Number of patients who are able to discontinue eltrombopag and dexamethasone with  $PLT \ge 30 \times 10^{9}/L$

- Number of patients with loss of response after treatment discontinuation
- Number of patients with bleeding events after treatment discontinuation
- Number of patients receiving rescue treatment

The descriptive primary analysis but not the logistic regression will be repeated in the subgroups mentioned in section 2.2.1 Subgroup of interest.

If a covariate lead to (quasi) complete separation of the model, the model will be modified. Then, this covariate will be skipped from the model.

### 2.6 Analysis of the key secondary objective

There is no key secondary objective. Thus this section is not applicable.

#### 2.6.1 Key secondary endpoint

Not applicable.

#### 2.6.2 Statistical hypothesis, model, and method of analysis

Not applicable.

#### 2.6.3 Handling of missing values/censoring/discontinuations

Not applicable.

### 2.7 Analysis of secondary efficacy objective(s)

#### 2.7.1 Secondary endpoints

For all analyses on secondary parameters the FAS is used unless it is specified otherwise.

The following parameters are analysed analogeously to the analysis of primary parameter respectively the supportive analyses on the primary parameter:

- 1) **Overall response** (OR), defined as number (%) of patients with platelet count  $\geq 30 \times 10^9$ /L and a 2-fold increase of screening  platelet count after treatment discontinuation in the absence of bleeding events  $\geq$  Grade II and no rescue therapy at all visits until Week 52 will be provided, analysis will be equivalent to the primary endpoint analysis
- 2) The duration of sustained response off treatment, median duration of response off treatment (weeks) counted from last dose of study treatment (eltrombopag or dexamethasone) until loss of response will be provided calculated using a Kaplan-Meier analysis based on the population
- 3) Overall response (OR) by week 4, presented by number (%) of patients with platelet count  $\ge 30 \times 10^{9}$ /L and a 2-fold increase of screening platelet count at least once

<sup>4 For patients who were pre-treated: the platelet count directly before start of pre-treatment

within the first 4 weeks without bleeding events  $\geq$  Grade II and no rescue therapy will be provided, analysis will be equivalent to the primary endpoint analysis.

- 4) Complete response (CR) by week 4, presented by Number (%) of patients with platelet count  $\geq 100 \times 10^{9}$ /L at least once within the first 4 weeks without bleeding events  $\geq$  Grade II and no rescue therapy will be provided, analysis will be equivalent to the primary endpoint analysis.
- 5) **Platelet count** from screening to 1, 2, 4, 12, 26 and 52 weeks; absolute and relative change in platelet count to screening, 1, 2, 4, 12, 26 and 52 weeks and EOS will be provided. Box plots for absolute and/or relative change in platelet counts from baseline to different time points will also be provided.
- 6) The **time to response for overall and complete response** using a Kaplan-Meier analysis.
- 7) The **duration of response for overall and complete response** using a Kaplan-Meier analysis. Here the following population is used: FAS patients who reached overall respectively complete response.
- 8) To evaluate patient HRQoL outcome measures for Health-Related Quality of Life (fatigue level of the patient through FACIT), FACT-Th6 and SF-36v2 questionnaires. Change in each domain score and total score of HRQoL parameters through FACIT and SF-36v2 questionnaires from baseline to 1, 2, 4, 12, 26, 52 weeks and EOS will be provided.
- 9) The incidence and severity of bleeding events

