12.1 Analysis sets

The Full Analysis Set (FAS) will consist of all patients to whom study treatment has been assigned by randomization. The FAS will serve as the primary analysis set for all efficacy analyses. According to the intent to treat principle, subjects will be analyzed according to the treatment they have been assigned to during the randomization procedure.

Before database lock, relevant protocol deviations and potential impact on analyses will be reviewed and adequately processed / documented.

The Safety Set (SAF) includes all subjects who received at least one dose of study treatment. Subjects in the SAF will be analyzed according to the study treatment actually received. Further details will be specified in the SAP.

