12.5 Analysis of secondary endpoints

For all efficacy and PRO analyses, the FAS will be used. For all safety analyses the safety set will be used.

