12.5.1 Efficacy endpoints

1. To compare the ability of eltrombopag in combination with a short course of high-dose dexamethasone **to induce overall response (OR)** after treatment discontinuation at week 52 versus a defined course of dexamethasone

Number (%) of patients with platelet count $\ge 30 \times 10^{9}$ /L and a 2-fold increase of screening platelet count after treatment discontinuation in the absence of bleeding events \ge Grade II and no rescue therapy at all visits until Week 52 will be provided, analysis will be equivalent to the primary endpoint analysis.

- 2. To assess the **duration of sustained response off treatment**, median duration of response off treatment (weeks) counted from last dose of study treatment (eltrombopag or dexamethasone) until loss of response will be calculated using a Kaplan-Meier analysis.
- 3. .
- 4. To assess the ability of eltrombopag to induce overall response (OR) by week 4

Number (%) of patients with platelet count $\ge 30 \times 10^9$ /L and a 2-fold increase of screening platelet count at least once within the first 4 weeks without bleeding events \ge Grade II and no rescue therapy will be provided, analysis will be equivalent to the primary endpoint analysis.

- 5. To assess the ability of eltrombopag to induce a **complete response (CR) by week 4** Number (%) of patients with platelet count $\geq 100 \times 10^{9}$ /L at least once within the first 4 weeks without bleeding events \geq Grade II and no rescue therapy will be provided, analysis will be equivalent to the primary endpoint analysis.
- 6. To assess the **platelet count** from screening to baseline and to 1, 2, 4, 12, 26 and 52 weeks; absolute and relative change in platelet count from screening to baseline and to 1, 2, 4, 12, 26 and 52 weeks and EOS will be provided. Box plots for absolute and/or relative change in platelet counts from screening to baseline and to different time points will also be provided.
- 7. To assess the time to response for overall and complete response using a Kaplan-Meier analysis.
- 8. To assess the duration of response for overall and complete response using a Kaplan-Meier analysis.

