# 4 Change to protocol specified analyses

No change from protocol specified analysis was made.

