#### 5.5.4 Duration of overall response

Overall response (OR) and time points reaching and loosing OR was assessed by the Data Review Committee, see data Review Meeting Minutes.

The following censoring rules are applied:

- If a patient does not loose overall response the duration is censored with the date of the last platelet assessment after Week 4
- If a patient does not respond initially by Week 4 (i.e. all platelet counts <30 G/L until Week 4) the interval is censored with 0 (days)

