#### 5.5.5 Duration of complete response

Complete response (CR) and time points reaching and loosing CR was assessed by the Data Review Committee, see data Review Meeting Minutes.

The following censoring rules are applied:

- If a patient does not loose complete response the interval is censored with the date of the last platelet assessment after Week 4
- If a patient does not respond completely initially by Week 4 (i.e. all platelet counts <100 G/L until Week 4) the interval is censored with 0 (days)

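### Duration of overall and complete response is restricted to responders without being declared as a departure from the protocol, so the by-arm curves are not a randomised comparison and need a label and a companion FAS table

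*SAP*

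**What the plan says.** Protocol 12.5 sets the population without exception: "For all efficacy and PRO analyses, the FAS will be used". Protocol 12.1 defines that set: "The Full Analysis Set (FAS) will consist of all patients to whom study treatment has been assigned by randomization". For this endpoint Protocol 12.5.1 gives only the method, with no limit to responders: "To assess the duration of response for overall and complete response using a Kaplan-Meier analysis".

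The SAP opens its list of secondary endpoints with a default that leaves room for exceptions: "For all analyses on secondary parameters the FAS is used unless it is specified otherwise". Item 7 of the same list (SAP 2.7.1) then uses that room: "Here the following population is used: FAS patients who reached overall respectively complete response". SAP 4 nevertheless states "No change from protocol specified analysis was made".

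The derivation sections point another way. For patients without an early overall response, SAP 5.5.4 has the rule "all platelet counts <30 G/L until Week 4) the interval is censored with 0 (days". SAP 5.5.5 has the counterpart for complete response: "all platelet counts <100 G/L until Week 4) the interval is censored with 0 (days".

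**The concern.** Reaching OR or CR happens after randomisation, and the trial's rationale is that adding eltrombopag produces more responders. Once the curve is limited to responders, the two groups are no longer comparable by randomisation. Suppose eltrombopag brings in patients who would not have responded to dexamethasone alone, and suppose their responses tend to be shorter. Those patients enter only the combination-arm curve and pull it down. Their counterparts on dexamethasone are absent, where they would otherwise count as having spent no time in response. The combination arm could then show a shorter duration among responders while its randomised patients spend more time in response on average.

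There is also a problem of documentation. Item 7 removes patients who never respond, 5.5.4 and 5.5.5 tell the programmer what to do with them, and SAP 4 says nothing departs from the protocol. Two programmers could produce tables with different denominators and both claim to follow the SAP.

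**Working it through.** The documents give no expected duration of response and no planning figure for this endpoint, so there is no plan figure to reproduce. All durations below are assumptions.

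**1. The passages side by side.** Protocol 12.5: FAS for all efficacy analyses. SAP 2.7.1 item 7: responders within the FAS. SAP 5.5.4/5.5.5: a rule for patients without response by Week 4, most of whom are outside item 7's set. SAP 4: no change. A patient who first responds after Week 4 fits item 7 but would be censored at 0 days under 5.5.4/5.5.5, so the two places disagree for that patient as well.

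**2. What censoring at day 0 does.** A patient censored at time 0 is never at risk at any later event time. Assumed example with 12 patients per arm and a 48-week horizon:
- Arm B (dexamethasone): 6 responders lasting 20, 28, 36, 44, 48+ and 48+ weeks.
- Arm A (combination): the same 6, plus 4 weak responders lasting 4, 6, 8 and 10 weeks.

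The sums are 224 weeks (B) and 224 + 28 = 252 weeks (A).

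| Handling of non-responders | Median B vs A | Mean B vs A |
|---|---|---|
| Left out (item 7) | 36 vs 20 | 224/6 = 37.3 vs 252/10 = 25.2 |
| FAS, censored at day 0 (5.5.4/5.5.5) | 36 vs 20 | 37.3 vs 25.2 |
| FAS, zero duration as an event | 0 vs 10 | 224/12 = 18.7 vs 252/12 = 21.0 |

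The first two rows are identical. Only the third credits arm A for its extra responders.

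**3. Near-worst-case size for CR.** Inputs: dexamethasone CR rate 50.5% (Protocol 4.3, high-dose dexamethasone arm of the cited trial). Assumed: combination CR rate 65% or 75%; duration = min(20·exp(bZ), 48) weeks with Z standard normal and b = 0.5 or 0.8; identical in both arms; patients with the highest Z respond first (correlation 1). The responder median is then 20·exp(b·z), where z is the normal quantile at 1 − p/2.

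| p | z | Median, b = 0.5 | Median, b = 0.8 |
|---|---|---|---|
| 50.5% | 0.667 | 27.9 | 34.1 |
| 65% | 0.454 | 25.1 | 28.7 |
| 75% | 0.319 | 23.5 | 25.8 |

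The apparent dexamethasone advantage runs from 27.9 − 25.1 = 2.8 to 34.1 − 25.8 = 8.3 weeks. By simulation (2 million draws), mean time in response per randomised patient is 15.3 to 17.8 weeks on dexamethasone and 17.9 to 21.6 on the combination, an advantage of about 2.5 to 4 weeks the other way. With equal response rates the gap is zero.

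**4. Relaxing the assumptions (same model).**
- Correlation 0.5 between responding and duration: CR gap 1.3 to 3.7 weeks. Correlation 0.3: 0.7 to 2.0 weeks.
- Correlation 0.5 and durations 15% longer on the combination: the reversal disappears in three of four scenarios, and the fourth is nearly a tie (27.3 vs 27.1 weeks).
- OR, dexamethasone 82.1% (Protocol 4.3), combination assumed 85% to 95%, correlation 1: gap 0.4 to 2.9 weeks.

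**5. A second model.** Assumed exponential durations, mean 40 weeks in common responders, 48-week horizon. The arm B median is 40·ln 2 = 27.7 weeks, and its mean time per randomised patient is 0.505 × 40(1 − exp(−48/40)) = 14.1 weeks. With 15 points of extra responders averaging 8 weeks and no other benefit, arm A has a responder median of 19.1 weeks but a mean per randomised patient of 14.1 + 0.15 × 8(1 − exp(−48/8)) = 15.3 weeks. If common responders also last 15% longer in arm A, the figures are 21.4 and 16.2 weeks, so the reversal persists. With an 82.1% OR rate, 5 extra points and the same 15% gain, it does not: the arm A median is 29.2 to 30.0 weeks.

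**The case against.** Several points on the other side are sound.

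- Protocol Table 2-1 words this objective as assessing duration, not comparing it. No log-rank test or hazard ratio is named. After Amendment 3, with about 24 patients expected, all analyses are descriptive (Protocol 12.8.1). A reader might infer that a formal between-arm conclusion is at risk; the documents plan none here.
- Duration has no natural value in a patient who never responded, and the protocol assigns none. Protocol 12.1 also calls the FAS the primary set for efficacy. Item 7 can be read as filling in an undefined detail, and a responder-only curve is a common summary. That justifies keeping the curve. It does not justify stating that nothing changed, or leaving 5.5.4/5.5.5 in conflict with item 7.
- A reader might infer that the gain in responders goes unreported. It does not: the primary endpoint, OR off treatment, and OR and CR by Week 4 are all reported on the FAS.
- The 3 to 8 weeks assume perfect correlation and no eltrombopag effect on duration, although arm A is treated for 26 weeks and arm B for at most 12. At 12 per arm, with an assumed 70% CR rate in arm A, the standard deviation of the difference in responder medians is about 6 to 10 weeks, larger than the average bias of about 4 to 7 weeks in the same model.

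What remains is that descriptive status does not remove selection bias from durations displayed by arm. In a trial this small, readers will look mainly at the point estimates.

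**Conclusion.** The point holds as a mismatch between protocol and SAP, together with a limit on interpretation. The responder restriction departs from Protocol 12.5 and is not declared in SAP 4. The day-0 censoring rule in SAP 5.5.4/5.5.5 conflicts with item 7 and, for patients who never respond, gives the same estimates as leaving them out. Durations shown by arm among responders are not a randomised comparison and can be biased against the arm with more responders.

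The size cannot be fixed from the documents. For CR it is about 3 to 8 weeks in the median under a near-worst-case assumption, about 1 to 4 weeks at moderate correlation, and 3 weeks or less for OR. It may be absent if eltrombopag also lengthens response. A reader might infer that the combination arm will look worse; that needs both a sizeable difference in response rates and clearly shorter responses in the added responders. What is affected is the reading of a descriptive secondary endpoint, not a confirmatory result.

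**What to change.** - **SAP 2.7.1 item 7:** keep the responder-only Kaplan-Meier curve, labelled as descriptive and not a randomised comparison.
- **SAP 4:** list the responder restriction as a departure from Protocol 12.5.
- **New FAS table, one per response type:** mean time in OR, and in CR, up to Week 53 per randomised patient by arm, with non-responders counted as 0 weeks, and the between-arm difference with a descriptive 95% CI. State how time after early withdrawal is treated.
- **SAP 5.5.4 and 5.5.5:** drop the day-0 censoring for the responder curve and count non-responders as zero duration in the FAS table. Say whether a first response after Week 4 counts. Changing the named population to the FAS is not enough on its own, because under day-0 censoring the estimates stay the same.

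No new data are needed. The cost is SAP wording, one extra table per response type, and a summary measure less familiar than a responder median. The mean is preferable to the median in the FAS table because, with zeros counted and a response rate near 50%, the median falls to about 0.

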#### 2.7.2 Statistical hypothesis, model, and method of analysis

Similar to the analysis of primary parameter (see 2.5.2) respectively supportive analyses of the primary parameter (see 2.5.4).

#### 2.7.3 Handling of missing values/censoring/discontinuations

Missing values are not replaced.

The time to response is censored with the date of the patient's last visit.

The duration of response is censored with the date of the patient's last visit.

#### 2.8 Safety analyses

The analysis of safety is described in section 12.5.2 of the CSP.

The population SAF is used for all safety analyses. All information obtained on safety data will be displayed by treatment group.

#### 2.8.1 Adverse events (AEs)

Only treatment-emergent AEs are included in the the safety analysis. Non-treatment emergent AEs are listed only in the Patient Data Listings (section 16.2.1 of the CSR).

Treatment-emergent adverse events (TEAE) are defined which started during the on-treatment period or increased in severity based on preferred term). The on-treatment period lasts from the

date of first dose of study treatment with eltrombopag or dexamethasone (whichever is first) to 30 days after the date of the last dose of study treatment (whichever is last).

The number (and percentage) of subjects with treatment-emergent adverse events will be summarized in the following ways:

- by treatment, primary system organ class and preferred term.
- by treatment, primary system organ class, preferred term and maximum severity (based on CTCAE grades).
- by treatment, Standardized MedDRA Query (SMQ) and preferred term

Separate summaries will be provided for study medication related AEs, death, SAEs, AEs leading to discontinuation and adverse events leading to dose adjustment.

The number (and proportion) of subjects with AEs of special interest (i.e. thromboembolic/ thrombotic complications, hepatobiliary laboratory abnormalities, bleeding, bone marrow reticulin formation and bone marrow fibrosis, and ocular changes) will be summarized by treatment.

A subject with multiple AEs within a primary system organ class is only counted once towards the total of the primary system organ class.

A subject with multiple AEs within a preferred term is only counted once towards the total of the preferred term class.

The incidence of AESIs will be summarized by SOC and Preferred Term (PT). In addition to the above mentioned analysis this analysis counts each AESI (which may occur multiple in one patient) but not only the occurrence in one patient/one SOC/one PT.

All deaths (on-treatment and post-treatment [starting at day 30+1 after last dose of eltrombopag]) will be summarized.

All AEs, deaths and SAEs will be listed and those collected during the pre-treatment (from day of patient's informed consent to the day before first dose of study treatment) and post-treatment period will be flagged.

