### 2.1.1 General definitions

**Study treatment** for patients randomized to the investigational combination treatment is eltrombopag until Week 26 in combination with 1 cycle of high-dose dexamethasone (subsequently referred to as treatment group ETB+DEX). For patients randomized to the control arm the study treatment consists of 1-3 cycles of high-dose dexamethasone (subsequently

referred to as treatment group DEX). These treatments will be called "study treatment" in the rest of the document.

When eltrombopag and/or dexame thas one will be given additionally, this is assessed as rescue or - if applicable - as concomitant medication during the data review meeting case-by-case.

The last available assessment on or before the date of start of eltrombopag is taken as "**baseline**" assessment. It is assumed that all assessments at Week 1/Day 1 are captured pre-dose on first day of eltrombopag (e.g. PROs), thus this Week 1/Day 1 is used for baseline when no screening values are available. Otherwise the screening values are considered as baseline. For all analyses on platelets the platelet count directly before pre-treatment will be used as baseline value in the pretreated patients. This is the more adequate way of taking into account the initial value at time of diagnosis and before pre-treatment for all patients

**Pre-treatment period**: from day of subject's informed consent to the day before first dose of study treatment.

**On-treatment period**: from date of first dose of study treatment to date of treatment discontinuation (including start and stop date).

**Treatment discontinuation** is the date of last study medication given as study treatment but not as rescue medication or not after after re-initiation, i.e. initial dose after failure of 1-3 DEX cycles (for details see Derivation of time point of treatment discontinuation5.1).

**Post-treatment period**: starting at day 30+1 after last dose of study treatment

The **Safety Follow-up period** specifies the observational period (30d) for which patients will be followed-up for safety events/measures.

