#### 2.8.3 Laboratory data

All laboratory data will be listed by treatment group, subject, and visit (including the safety follow-up visits). Values outside the center-specific normal range are flagged as "low" or "high", as well as clinically significant abnormalities and CTCAE grades, if applicable. Summary statistics will be provided by treatment group and visit. Changes are calculated from baseline to the last on-treatment value. Again (see Adverse events (AEs)2.8.1) the on-treatment period lasts from the date of first dose of study treatment with eltrombopag or dexamethasone

(whichever is first) to 30 days after the date of the last dose of study treatment (whichever is last).

Boxplots will be presented for the total study course separated by treatment group in addition.

Grading of laboratory values will be assigned programmatically as per NCI Common Terminology Criteria for Adverse Events (CTCAE) version 5.0. The calculation of CTCAE grades will be based on the observed laboratory values only, clinical assessments will not be taken into account. CTCAE Grade 0 will be assigned for all non-missing values not graded as 1 or higher. Grade 5 will not be used. For laboratory tests where grades are not defined by CTCAE v5.0, results will be categorized as low/normal/high based on laboratory normal ranges.

For laboratory tests where grades are defined by CTCAE v5.0,

- Worst post-baseline CTCAE grade (regardless of the baseline status). Each subject will be counted only once for the worst grade observed post-baseline.
- Shift tables using CTCAE v5.0 grades to compare baseline to the worst on-treatment value

For laboratory tests where grades are not defined by CTCAE v5.0,

Shift tables using the low/normal/high/ (low and high) classification to compare baseline to the worst on-treatment value.

Any significant findings in laboratory will be documented as AEs and reported as such. Laboratory data reported in the eCRF section of Adverse Events (labeled as "relevant laboratory results regarding this AE") are listed only.

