# 5 Appendix

### 5.1 Derivation of time point of treatment discontinuation

The time point of **treatment discontinuation** is the date of last dose of study medication given as study treatment but not as rescue medication, not after re-initiation or not after as initial dose after failure of 1-3 DEx cycles, and not as concomitant medication (if applicable).

For patients randomized to DEX monotherapy the time point of treatment discontinuation is the date of last study medication dexamethasone documented on the "End of Treatment" CRF. During the data review meeting it will be verified, that this date corresponds to the stop of study treatment but not to the stop of rescue medication.

For patients randomized to ETX+DEX combination therapy the time point of treatment discontinuation is the maximum date of the study medications eltrombopag and dexamethasone documented on the "End of Treatment" CRF, in general. When the primary reason for permanent discontinuation of eltrombopag is:

- "stop of eltrombopag re-initiated after relapse", or
- "stop of eltrombopag as rescue medication for patients randomized to DEX monotherapy" or
- the free text specification of "other reason" indicate that elthombopag was re-initiated or used after switch from DEX to ETB

the stop of study treatment eltrombopag has to be visually assessed from the data of the "Eltrombopag – Dosage Administration Form" during the data review meeting.

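### As SAP 2.1.1 and 5.1 define study treatment, the TEAE window closes 30 days after the randomised course, so AEs starting later under crossover or re-started eltrombopag are listed but not tabulated

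*SAP*

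**What the plan says.** SAP 2.8.1 summarises only treatment-emergent AEs. Other AEs appear in the patient listings, with post-treatment ones flagged. The window opens at the first dose of eltrombopag or dexamethasone, whichever comes earlier, and runs "to 30 days after the date of the last dose of study treatment (whichever is last".

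SAP 2.1.1 fixes what study treatment means for the rest of the SAP. In Arm A it is eltrombopag until Week 26 plus one dexamethasone cycle. In Arm B: "For patients randomized to the control arm the study treatment consists of 1-3 cycles of high-dose dexamethasone". If more of either drug is given, "this is assessed as rescue or - if applicable - as concomitant medication during the data review meeting case-by-case". SAP 5.1 dates treatment discontinuation by the last dose given as study treatment, "not after re-initiation or not after as initial dose after failure of 1-3 DEx cycles", and not as rescue or concomitant medication. For Arm A it takes, in general, "the maximum date of the study medications eltrombopag and dexamethasone documented on the" End of Treatment form, and leaves re-initiation cases to visual assessment at the data review meeting.

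The on-treatment period has two definitions. SAP 2.1.1 runs it "from date of first dose of study treatment to date of treatment discontinuation (including start and stop date". SAP 2.8.1 and 2.8.3 use the same name for a period that lasts 30 days longer. For laboratory data, "Changes are calculated from baseline to the last on-treatment value". Post-treatment deaths are counted "starting at day 30+1 after last dose of eltrombopag".

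The protocol (section 3, Tables 6-1 and 6-2, section 6.1.4) provides eltrombopag to Week 52 for Arm B patients who fail or relapse and for Arm A patients who relapse. Protocol 12.5.2 lets safety tables run to 30 days after the last visit, but limits AE tables to an on-treatment period that it does not define.

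**The concern.** Eltrombopag is the drug whose safety the trial sets out to describe, and for Arm B patients who cross over this is their first exposure to it. The SAP recognises this dosing: section 2.4.1 summarises mean dose for patients treated beyond Week 27 or Week 13. It plans no matching AE table. With study treatment limited to the randomised course, SAEs, thromboembolic events and hepatobiliary AESIs that begin under later eltrombopag can fall outside every AE summary table. The laboratory change and on-treatment shift tables share the cut-off.

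Other wording supports a wider window: the eltrombopag-or-dexamethasone phrasing in SAP 2.8.1, protocol 9.2 (patients still on study treatment at W53D1) and the protocol glossary. That reading creates a different problem. SAP 2.8 displays safety by treatment group, only ETB+DEX and DEX are defined, and the Safety Set (SAP 2.2) classifies whole subjects rather than periods. By inference, AEs under crossover eltrombopag would then appear in the DEX column.

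**Working it through.** The documents give no window length, so there is no stated figure to reproduce. The check is date arithmetic, with day 1 the first dose, Week 26 ending on day 182, Week 52 ending on day 364 and W53D1 on day 365.

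**Inputs.** Arm B: one to three 4-day cycles, 4 weeks apart (14 to 28 days allowed), at most 12 weeks (protocol 6.1, 6.1.4). Arm A: 26 weeks (protocol 6.1.4). Window: last study-treatment dose L plus 30 days (SAP 2.8.1). AE collection: 30 days after the later of last dose or last visit (protocol 10.1.1), so 365 + 30 = day 395.

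**Window end on the narrow reading.** In Arm B, L = (cycles − 1) × interval + 4. The window ends on day L + 30, and 395 − (L + 30) days of AE collection lie outside it.

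| Case | L | Window end | Weeks | Days outside |
|---|---|---|---|---|
| B, one cycle | 4 | 34 | 4.9 | 361 |
| B, three cycles, 14 days apart | 32 | 62 | 8.9 | 333 |
| B, three cycles, 28 days apart | 60 | 90 | 12.9 | 305 |
| B, dosing at 12-week ceiling | 84 | 114 | 16.3 | 281 |
| A, completes 26 weeks | 182 | 212 | 30.3 | 183 |

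**Share of later-eltrombopag days outside the window (illustrative).**
- Arm B, three 4-weekly cycles, eltrombopag from day 61 to day 364 without a break: 304 days, of which 364 − 90 = 274 are outside; 274/304 = 90%.
- Arm A, eltrombopag from day 183 to day 364: 182 days, of which 364 − 212 = 152 are outside; 152/182 = 84%.
- An assumed 42-day course started at once: 30 days inside, 12 outside; 12/42 = 29%. Started 14 days later: 30 − 14 = 16 inside, 26 outside; 26/42 = 62%. The 42 days (2 weeks at 50 mg, 4 weeks at 75 mg) borrow the Table 6-1 stop. Protocol 6.5.1 refers crossover dosing to Table 6-4, so this is only an example.
- Any course starting more than 30 days after the last randomised dose: 100%.

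**Wider reading (illustrative).** For the same Arm B patient treated to day 364, the window runs to 364 + 30 = day 394, and 304/394 = 77% of its days are eltrombopag days.

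**Eltrombopag continued after a taper relapse in Arm A.** SAP 2.1.1 stops study treatment at Week 26, which gives 182 + 30 = day 212. If the general rule in SAP 5.1 applies and dosing runs to Week 52, the end is 364 + 30 = day 394. The SAP does not settle which holds.

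**Death anchor.** Arm B patients who never cross over have no last eltrombopag dose. In a crossover patient, on the narrow reading, a death under later eltrombopag after L + 30 is neither on-treatment nor, by this anchor, post-treatment.

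**The case against.** The strongest reply is that the randomised course plus 30 days is a defensible TEAE window: it largely keeps crossover exposure out of the randomised comparison. This stands, and it is a reason to keep those tables. It does not explain why later eltrombopag has no table of its own. Nor is the separation complete: an AE starting under crossover eltrombopag within 30 days of the last dexamethasone dose is inside the window anyway.

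It is also fair that the analysis is descriptive with about 24 patients, that all AEs and SAEs are listed, that all deaths are summarised, that WHO bleeding is tabulated after treatment (SAP 2.8.4.1), and that by-visit laboratory data and worst post-baseline grade extend further. The gap is therefore confined to the AE, SAE and AESI summaries and the laboratory change and on-treatment shift tables. In a descriptive trial, however, those tables are the main safety output.

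A reader might infer that the SAP directs crossover AEs into the DEX column or attributes them to dexamethasone. It does not say so. Pooling is an inference, treatment actually received is judged at the data review meeting, and investigators record the relationship to eltrombopag and/or dexamethasone (protocol 10.1.1). A reader might also infer that the statement of no change in SAP section 4 is wrong. Protocol 12.5.2 sets an outer limit and itself restricts AE tables to the on-treatment period, so a departure is not shown.

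**Conclusion.** The point holds as a should-fix. On the SAP's own definitions, the AE tables close at about day 34 to 90 in Arm B on the stated cycle schedule (day 114 at the ceiling) and at day 212 for an Arm A completer. Planned eltrombopag to Week 52 can lie largely beyond that. The two definitions of the on-treatment period conflict on any reading, and the death anchor does not suit Arm B.

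The 90%, 84% and 77% figures assume later eltrombopag that starts at once and runs unbroken to Week 52. They should not be read as expected values, since shorter or delayed courses give anything from 29% to 100% in the cases above. They count days, not events. The documents do not say how many patients took later eltrombopag. As a rough guide only, 12 per arm at the planning response rates gives 12 × 0.70 = 8.4 non-responders in Arm B and 12 × 0.35 = 4.2 in Arm A, and not all of these would receive it. Nor do the documents fix day 394 for a taper relapse in Arm A: SAP 5.1 applies its maximum-date rule only in general.

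**What to change.** - Use one definition of the on-treatment period, or two different names, across SAP 2.1.1, 2.8.1 and 2.8.3.
- Keep the tables for the randomised course plus 30 days.
- Add separate AE, SAE and AESI tables for later eltrombopag (crossover, continued or re-started) plus 30 days, not pooled into the DEX column, with the number of patients and patient-time in that period.
- State a rule for days on which the two periods overlap, and say to which period eltrombopag continued after a taper relapse belongs.
- Anchor post-treatment deaths to the last dose of any study drug.
- Reconcile the window with protocol 12.5.2 and record any difference in SAP section 4.

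The cost is SAP wording and a few more tables. The AE data are already collected. The downside is small cells, which should be shown as counts with patient-time rather than compared.
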